Hebert and colleagues randomized 838 critically ill patients to either a liberal protocol in which transfusions were administered to maintain hemoglobin levels above 9 g/dl, or a restrictive strategy in which hemoglobin levels were kept between 7 and 9 g/dl. Overall, the 30-day mortality rate was 19 % in the restrictive group and 23 % in the liberal transfusion group (p=NS). [11]

On the other hand, anemia can also cause a potential increase in morbidity and mortality in critically ill patients, and in ECMO is an even greater critical issue in reducing delivery of oxygen (DO₂). [12, 13] Moreover, despite improvement in technology and care, complications related to ECMO are still high, and frequently involve an imbalance in the coagulation status due to anticoagulant use in the presence of coagulopathy [14-16]. Consequently, the risk of thrombosis (presumably microthrombosis) and hemorrhage remain to be high [17-20]. In the case of ongoing bleeding, transfusion of Packed Red Blood Cell (PRBC) is required to support desired haemoglobin levels [21, 22].

Traditionally, the threshold for PRBC transfusions in ECMO is aimed to maintain hemoglobin (Hb) values in the normal range (12-14 g/dL) [23]. Despite this, there is considerable uncertainty regarding the optimal haemoglobin threshold for the use of PRBC transfusions in anemic patients during ECMO support.

Prompted by the general reappraisal of PRBC transfusion use, some case series using lower target for Hb during vv-ECMO support have been published [24-26]. However, such protocols do not use/suggest a definitive trigger/target of Hb [27].

There is also some evidence that a higher number of transfusions in ECMO patients is associated with worse outcomes [28-30]. However, such a relationship is difficult to assess given the large

number of factors influencing transfusion practice in this setting: target of anticoagulation, frequent bleeding episodes, the peculiar characteristics of the circuits that can cause mechanical damage, activation of inflammation, and consumption of platelet and coagulation factors, to name but a few [31].

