Moreover, most of the available data on transfusions during ECMO are heterogeneous, usually including VV-ECMO and veno-arterial-ECMO (VA-ECMO) configuration, and mixing adults with neonatal and pediatric cohorts, which are historically more represented. Recently, a meta-analysis including 1042 patients presenting refractory ARDS and focusing on complication rate and hospital mortality associated with VV-ECMO showed a limited impact of bleeding and total number of haemo-derivates administrated on patient outcome. [32]

In this context, the decision of giving a transfusion during ECMO support is still a real challenge since several parameters have to be taken into account at the same time. A strict trigger has not yet been defined in this population, and the literature on critically ill patients suggests a relevant reduction in the amount of transfusion.

Rationale for the study

Providing adequate DO₂ can be approached in several ways during vv-ECMO support, but the hemoglobin target is always a critical point, and a relevant piece of the puzzle of assuring the best oxygenation in patients affected with acute respiratory failure (ARF). There may be important variations between hospitals and countries in the use of PRBC transfusions, which may impact patient outcome. Large scale, national, and international studies are currently lacking.

While there are extensive reviews on predicted ECMO survival, and management (even with many debated issues), there is a significant knowledge gap in understanding the benefits and risks of transfusion during VV-ECMO. [30, 33, 34]

An international multicenter study will evaluate prospective observational data of transfusion practices during VV-ECMO for ARF, analyzing it in light of anticoagulation and bleeding episodes.

Aim of the study

The PROTECMO study is aimed at being a collaborative study including a large number of ECMO centers worldwide, describing, in real practice,

- 1) Incidence of major bleeding events and amount of blood product transfused
- 2) Type, trigger and level of anticoagulation adopted

The descriptive variable end points for the primary aim will be the daily and the total amount of PRBC and other blood products (Plasma, Platelets, Fibrinogen, Antithrombin III).

The descriptive variable end points for the secondary aim will be the type and dose of anticoagulation, and episodes of bleeding according to site and severity.

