ECMO management data will be collected daily for the first 28 days. Additionally, fluid balance, adverse events, Hb and all hematological data, anticoagulation management and monitoring will be collected every 24 hours.

Data will also be collected for the duration of mechanical ventilation, duration of ECMO, and ICU length of stay. Clinical outcome assessment will be made, with date of death, ICU discharge, hospital discharge, sixth month mortality.

Statistical Analysis

Descriptive statistics including frequency (percentage), median and interquartile range (IQR) will describe overall population and groups of survivors and non-survivors.

In order to describe current transfusion practice the amount of PRBC, Plasma and Platelets, will be described as units and ml and as a number of transfusions adjusted for ECMO length of stay and considering the concomitant bleeding episodes.

Fibrinogen and Antithrombin III will be described as mg or units respectively and as a number of administration.

Anticoagulation will be reported as type, mean dosage and the confidence interval (CI 95%).

Hb average level and the confidence interval (CI 95%) will be reported.

Baseline categorical and continuous variables will be compared for transfusion and ECMO weaning groups. In particular categorical variables will be compared with chi-square tests and continuous variables will be compared with Student's T-test, or Wilcoxon rank-sum tests, otherwise.

Multiple COX regression analysis will be used in order to explore the impact of confounding factors such as baseline patient severity, ECMO length of stay, bleeding episodes and possible others covariates and factors that will be observed and raised relevance during the first exploratory or univariate analysis. The impact of relevant confounding factors such as length of ECMO run, pre-ECMO severity scores, pre-ECMO administration of transfusions will be analyzed separately and together in multiple analyses.

In particular daily RBC transfusion will be studied according to the association to renal function, fluid balance, worst Hb level, episodes of bleeding, use of vasopressors, ECMO blood flow.

A p-value less of than 0.05 will be considered significant. Data handling and analyses will be done with SAS 9.4 software (SAS Institute Inc, Cary, NC, USA) and R 3.3 software (R Foundation for Statistical Computing).

Patient data Collection

For each included patient the investigators will collect the following data:

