1. Clinical data

- Demographics: age, gender, weight, height, BMI
- Pre-existing pulmonary disease: asthma, cystic fibrosis, chronic obstructive pulmonary disease, pulmonary hypertension, pulmonary fibrosis, chronic restrictive lung disease
- Main co-morbidities: diabetes mellitus, chronic renal failure, ischemic heart disease, heart failure, chronic liver failure, neurological impairment
- Cause of ARF: bacterial pneumonia, viral pneumonia, trauma/burns, aspiration pneumonia, pancreatitis, pulmonary vasculitis, post lung transplantation
- Diagnosis: ARDS, Chronic end stage respiratory disease
- Postoperative period < 7 days. Pregnancy or peri-partum.
- Pre-ECMO hospital/ICU length of stay, mechanical ventilation days
- Patient characteristics at ICU admission: SAPS 2, SOFA score, PaO₂/FiO₂ ratio, hematocrit, platelets
- ECMO severity scores: PRESERVE score, RESP Score, ECMOnet if appropriate

2. ECMO and daily management data

- Type of circuit: heparin-bonded or not, type of oxygenator
- Type of anticoagulation: heparin, bivalirudin, argatroban, no anticoagulant

- Dose of anticoagulation
- Amount of PRBC, Plasma, platelets transfused (unit and ml) the day before
- Eventual Fibrinogen administration (mg)
- Antithrombin III level
- Antithrombin III administration (Type: human plasma-derived, recombinant) and dosage
- Episodes of bleeding classified according to site (airway – including tracheotomy - oro-nasal, gastric, intrathoracic, abdominal, intestinal, retroperitoneal, urinary tract, other) and severity according to 5 adjusted categories of the Bleeding Academic Research Consortium (BARC) score: Type 0, no bleeding; Type 1, Any overt bleeding that requires heparin infusion rate reduction or PRBC transfusion (provided Hb drop was related to bleeding); Type 2, any overt bleeding that requires heparin infusion rate reduction and packed red blood cells transfusion or non-surgical procedure to stop bleeding (provided Hb drop was related to bleeding); Type 3, Any life-threatening bleeding that required PRBC transfusion and surgical intervention for control of bleeding or ECMO discontinuation; Type 4: any fatal bleeding
- Daily blood and air flow, ECMO FiO₂
- 24 hours diuresis and fluid balance
- Use of continuous renal replacement therapy
- Mean arterial pressure, use of vasopressors
- Septic shock
- Hemoglobin, hematocrit, platelet count, fibrinogen if available.
- Daily gas exchange: pH, PaO₂, PaCO₂, SaO₂

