There will be no additional interventions or measurements other than those that are standard of care at the participating center. All clinical activity will follow the well established protocols for ECMO support at each participating center and consequently the patients are at no risk by in participating in the study.

Given the observational nature of the study, no insurance is required.

Predefined subgroup analyses

If the sample size will be adequate, as explorative analyses, we will perform some subgroup analyses according to the following predefined plan.

Exploratory analyses will stratify data for center workload (<10, 10-20, >20 ECMO run per year), according to geographical areas (we imagine a stratification among continents but we will verify if, giving the amount of data, will be reasonable a country stratification), and for pre-ECMO severity scores (Preserve score and Respscore) divided in quartiles.

Moreover, by the repeated measurements of hemoglobin and eventual transfusion event, for each center we will profile the actual and effective hemoglobin accepted as a trigger. The outcome weaning from ECMO and effective ICU discharge will be stratified also according to different hemoglobin values (<7, 7-10, >10, >12).

Another subgroups analysis will involve age, considered a major impacting factor in survival during ECMO. Patients will be divided in quartiles and patients > 60 years old will moreover evaluated.

Jehovah's witnesses and all patients refusing transfusions for personal reasons, as well as patients affected with hematological malignances will be analyzed separately.

Effective resources to implement the project

The study will be coordinated by IRCCS-ISMETT (Istituto Mediterraneo per I Trapianti e Terapie ad alta specializzazione).

Throught the REDCAP database, data will be collected and then analyzed at ISMETT.

The study has received the endorsement of the European Society of Intensive Care Medicine (ESICM) and the International ECMO network.

Professional statisticians and data manager at ISMETT will work on the project assuring proper data handling and performing the interim and final analyses.

No financial support is currently available.

Expected results, potential benefit of the study and publication program

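### Weaning and ICU discharge are stratified by an undefined haemoglobin measure without adjustment, so severity and bleeding can create, mask or reverse a gradient

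*Combined protocol and SAP*

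**What the plan says.** All places are in the combined protocol and SAP.

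- **Predefined subgroup analyses** opens with a condition: "If the sample size will be adequate, as explorative analyses, we will perform some subgroup analyses according to the following predefined plan". It then says that "for each center we will profile the actual and effective hemoglobin accepted as a trigger", and the next sentence reads "The outcome weaning from ECMO and effective ICU discharge will be stratified also according to different hemoglobin values", with bands <7, 7-10, >10 and >12. No haemoglobin measure, time window, covariate or test is given. Quartiles of the pre-ECMO severity scores are a separate stratification and are not crossed with haemoglobin.
- **Statistical Analysis** plans a multiple Cox regression with baseline severity, length of ECMO and bleeding among its factors, and adds: "The impact of relevant confounding factors such as length of ECMO run, pre-ECMO severity scores, pre-ECMO administration of transfusions" are to be examined singly and jointly. It states neither the event nor the exposure, and it does not mention the haemoglobin strata. A general 0.05 significance level applies.
- **Background** explains that the link between transfusion and outcome is hard to assess because of the "number of factors influencing transfusion practice in this setting: target of anticoagulation, frequent bleeding episodes" and circuit effects.
- **Rationale for the study** names the practice question: "There may be important variations between hospitals and countries in the use of PRBC transfusions, which may impact patient outcome".
- **Patient data Collection** includes "ECMO severity scores: PRESERVE score, RESP Score, ECMOnet if appropriate", age, daily haemoglobin, daily bleeding by site and grade, weaning (yes/no) and ICU discharge (yes/no, with date).

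**The concern.** Haemoglobin during an ECMO run is partly a result of how the patient is doing. The plan's bleeding grades 1 and 2 refer to a bleeding-related fall in haemoglobin, and its listed reasons for transfusion include haemodynamic impairment and low ECMO blood flow. Bleeding and severity plausibly also affect weaning and ICU discharge. A bleeding patient held at 9 g/dL with many units and a stable, untransfused patient at 9 g/dL would fall in the same stratum.

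If the strata use patient-level haemoglobin, a difference in weaning across bands may reflect who is in each band and not any effect of haemoglobin. The study is motivated by uncertainty about haemoglobin targets, so a crude gradient in either direction could be read as evidence on those targets.

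**Working it through.** **1. The plan's own figures.** Study conduction gives no sample-size calculation, only a projection: at least 100 patients in Italy at 10 or more per centre, and at least double worldwide. That implies 100 / 10 = 10 Italian centres and 2 × 100 = 200 patients. There is no outcome rate, effect size or power for the haemoglobin table, so there is nothing further to reproduce.

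**2. Simulation with no haemoglobin effect.** From the plan: N = 200, the band limits (made exclusive as <7, 7-10, 10-12, >12) and the 0.05 level. Everything else is assumed:

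- 20 centres, with a trigger uniform on 7-10 g/dL and unrelated to case mix
- severity S standard normal; bleeding B with P(B = 1) = expit(-0.6 + 0.5·S)
- haemoglobin = trigger + 1.5 - a·S - b·B + N(0,1)
- logit P(weaned) = 0.9 - ln(OR_S)·S - ln(OR_B)·B, with no haemoglobin or trigger term
- test: 1-df logistic likelihood-ratio trend over bands, without and with S and B in the model

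Weaned (%) by band, and share of studies with p<0.05:

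| Scenario | a, b | OR_S, OR_B | <7 | 7-10 | 10-12 | >12 | Unadjusted | Adjusted |
|---|---|---|---|---|---|---|---|---|
| Hb unrelated to S, B | 0, 0 | 2, 2 | 64.5 | 63.9 | 63.8 | 63.9 | 4.8% | 5.7% |
| Weak links | 0.2, 0.3 | 1.5, 1.5 | 61.0 | 65.9 | 68.4 | 71.1 | 7.1% | 4.1% |
| Bleeding only | 0, 0.7 | 1, 2 | 59.5 | 64.1 | 66.7 | 68.4 | 8.1% | 5.3% |
| Moderate | 0.4, 0.7 | 1.8, 2 | 47.7 | 60.4 | 68.5 | 75.4 | 35.1% | 4.5% |
| Strong | 0.6, 1.0 | 2.2, 2.5 | 36.4 | 56.1 | 70.1 | 80.2 | 79.5% | 5.9% |
| Sicker kept at higher Hb | -0.4, 0 | 1.8, 2 | 74.6 | 67.1 | 61.8 | 56.1 | 18.9% | 6.2% |
| Offsetting links | -0.3, 0.9 | 1.8, 2 | 63.6 | 64.2 | 64.4 | 64.3 | 5.2% | 4.9% |

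The first five rows use 1,500 studies each and the last two 1,000. At 1,000 studies the Monte Carlo standard error at 5% is √(0.05 × 0.95 / 1000) = 0.7 percentage points, so the adjusted rates are compatible with 5%. In the moderate case at N = 400 (800 studies), the unadjusted rate rises to 65.1% and the adjusted rate is 3.8%. More patients make the false signal more likely.

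**3. Centre trigger as the stratifier.** With the trigger spread over an assumed 6.5-12.5 g/dL, unrelated to case mix, and the moderate links, weaning is 63.9, 64.2, 64.2 and 64.2% across the bands. The unadjusted rejection rate is 5.0%.

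**4. The bands.** As printed, a value above 12 belongs to both >10 and >12. In the seven scenarios, 1.0% to 4.7% of patients fall below 7, which is 2 to 9 of 200, so that stratum would be very imprecise.

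**The case against.** Several points on the other side are sound.

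- **Which haemoglobin.** A reader might infer that the strata use each patient's attained value. The text does not say so. The sentence directly before is about the centre's trigger, and on that reading most patient-level confounding falls away (step 3), although centre case mix could still differ. This stands, and it makes the missing definition the first thing to repair.
- **Certainty of a false gradient.** A reader might infer that the table is bound to show a relation. It is not. Under weak links the rejection rate is 7.1%, under offsetting links it is 5.2%, and if sicker patients are kept at higher haemoglobin the gradient reverses. This stands; but an unpredictable direction does not make the crude table easier to read.
- **Adjustment elsewhere.** The Cox model includes severity and bleeding and leaves room for further covariates, so haemoglobin could enter it. It would be wrong to say that the plan has no adjustment. But that model names no event or exposure, and nothing ties it to this table.
- **Other links between haemoglobin and outcome.** A reader might take this for the only such analysis. Statistical Analysis also compares baseline variables between weaning groups, and the baseline data include haemoglobin and ICU-admission haematocrit. Those comparisons are also unadjusted.
- **Status.** The table is exploratory and conditional on sample size, no test is assigned to it, and no sentence commits to a causal or threshold claim. This limits the weight of the point. It does not tell a reader how to interpret a gradient if one appears.

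**Conclusion.** The point holds in a limited form. The plan stratifies two patient outcomes by haemoglobin without defining the measure and without adjustment, and its regression is not connected to that table. On a patient-level reading, severity and bleeding can produce, hide or reverse a gradient when haemoglobin has no effect. At 200 patients the simulated false-positive rate runs from 5% to 80% unadjusted and from 4% to 6% adjusted.

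These figures show what can happen and do not predict this study. The weaning rate, the bleeding rate, the haemoglobin shifts, the odds ratios and the trend test are all assumed. ICU discharge was not simulated. The adjusted model is a best case, because it contains exactly the severity and bleeding variables that generated the outcome, measured without error.

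The primary descriptive aims are not affected. The correction is worth making before analysis because adjusting for a severity score and age, both already collected, is a cheap improvement on crude strata. The bleeding term can be used only once an index haemoglobin has been defined.

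**What to change.** In Predefined subgroup analyses:

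1. Define the index haemoglobin (for example baseline, or the mean over a stated window) and its time window. A worst value over the whole run should not be left as the default, since longer runs give more measurements and so more chance of a low one.
2. Make the bands exclusive, for example by replacing >10 with >10 to 12, and assign the boundary values.
3. Label the crude table descriptive, without p-values.
4. Base any statement or p-value on haemoglobin and weaning or ICU discharge on a stated regression adjusted for pre-ECMO RESP or PRESERVE score, age, and bleeding before the index haemoglobin.
5. As a secondary view, report both outcomes by the centre's profiled trigger with the same case-mix adjustment, allowing for clustering by centre.
6. Acknowledge that bleeding and haemoglobin management influence each other over time, so one regression leaves residual time-varying confounding.

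**Cost.** SAP wording and one or two extra models. The severity scores, age, daily haemoglobin, daily bleeding and both outcomes are already on the collection list. The centre-level view will have wide intervals with few centres, and its trigger profile depends on transfusion-event data that are collected only where local practice provides them.
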